### Intervention

Participants in the intervention group will participate in 8 weekly telephone sessions with an interventionist. The telephone-based intervention consists of a problem-solving telephone support educational intervention led by a trained interventionist. The intervention’s main objective is to reduce caregiver burden and depressive symptoms by teaching caregivers a creative and optimistic approach to solving caregiving related problems. The intervention will utilize the problem solving module and refer to additional information/tools on the Spanish RESCUE website (<http://www.cidrr8.research.va.gov/rescue-espanol/>). The information included in the intervention consists of: 1. Introduction, 2. Illustrative Example, 3. Individualized Practice Exercise, and 4. Summary.

The intervention is adapted from the intervention used in our previous pilot project and based on the work of Bakas et al.,[23] who conducted a successful 8-week telephone intervention which used support approach and a task skill-building kit (TASK). In this proposed project we will tailor our pilot intervention to be culturally relevant for a Puerto Rican population. The intervention was developed to reflect specific characteristics of the target population such as language, cultural values and norms, and degree of acculturation. To enhance the cultural relevance of the intervention, we will use findings from our previous projects and guidelines from authoritative sources [55] that recommend: 1) involving persons from the target population in all phases of the project (e.g., Advisory Consortium), 2) emphasizing themes that are valued by the PR culture (e.g., family, religion, self-reliance), 3) assuring that the language and wording of on-line information is low-literate and appropriate by enlisting services of certified translators and Spanish-speaking experts, and 4) conducting the intervention and assessments by hiring research staff members (i.e., interventionist, data collector) who are Hispanic, fluent in Spanish, and knowledgeable about the PR culture. Research consistently shows that matching interventions to the individual needs of participants is more effective in engaging adults and modifying behaviors than prescriptive approaches.,[16] Other studies underscore the benefits of interventions and programs that are tailored to a specific race/ethnic populations.[55]

The intervention is described in detail in the table below. Based on prior studies, we anticipate that the calls will last between 45-60 minutes. However, the length of the calls will vary depending on the needs of the caregivers. We will document the length of the calls and adjust for this dose-response effect in the analysis. 10% of participants will have an intervention session recorded for quality assurance and training purpose. No session will be recorded without first informing the participant and obtaining their oral consent for the recording (see fidelity considerations below).

### **Telephone/Internet Intervention: Topical Content**

|  |  |
|--|--|
| 
Topic 1: Introduction
 
Tour of the Spanish RESCUE Website and Orientation to the Problem-Solving Method (Session 1)
   | 
Step one: The interventionists will establish rapport with an "ice breaker" by asking the caregivers to talk about their families and what they enjoy doing at home.
 
Step two: The interventionists will review the content in the RESCUE workbook that the caregivers will have received in the mail. On the front of the workbook will be RESCUE stroke caregiver website logo, the URL, and the telephone # of the VA National Caregiver Support Line. Inside, the workbook will be the following: 1) directions for using the unique URL to access various materials on the RESCUE website, 2) details of the study with the name/phone numbers of the PI and PC, 3) calendar with the mutually-agreed dates and times for the intervention sessions and for the post-test assessment, 4) problem-solving diary, 5) copy of the written statement, 6) summary of the steps of the problem-solving approach for easy reference when the caregivers are away from their computers, and 7) a brief note thanking them for their participation accompanied by a motivational message to keep updating their plans. The interventionists will emphasize that the caregivers should only access the RESCUE website using their unique URLs, so we can track usage and gather study statistics.
 
Step three: The interventionists will tell the caregivers to log-onto the RESCUE website following directions in the workbook. The interventionists will give a tour of the various features on the RESCUE website as the caregivers simultaneously navigate and explore the website.
 
Step four: The interventionists will direct the caregiver to click on and open the problem-solving module (available on RESCUE website). Similar to how teachers use power-point presentations for classroom instruction, the interventionists will use the module to teach the problem-solving method.
 
Step five: The interventionists will discuss the basic premises of the problem-solving approach. Problems are successfully handled by developing a Creative and Optimistic way of thinking. The Problem-solving approach is effective and involves the following steps: 1) identifying & defining problems; 2) prioritizing problems; 3) selecting the highest priority problem; 4) gathering Expert information; 5) setting realistic goals; 6) listing all possible solutions; 7) choosing the best solution; and 8) evaluating the plan.
 
Step six: Prior to moving to the next part of the module, the interventionists will ask scripted questions to determine the caregivers' understanding and will clarify information as needed.
 |
| 
Topic 2: Illustrative Example
 
How to use the problem-solving approach and the RESCUE website to address a common caregiver problem – STRESS & DEPRESSION (Session 2)
 | 
Step one: The interventionists will next illustrate how to apply the problem-solving method. To accomplish this, the interventionists will ask the caregivers to open the factsheet, titled "Caregiver Stress and Depression" on the website and read along as they discuss the key points. We chose "Caregiver Stress and Depression" as an illustrative topic because our previous research has shown that over 45% of caregivers of Veterans with strokes scored above the clinical cut-off for depressive symptoms.[55] All RESCUE website factsheets are organized in the COPE framework and include: 1) common signs/symptoms that caregivers should look for, 2) information that there are effective treatments, 3) helpful tips, and 4) information on when and where to seek emergency help or when to call their healthcare provider. In addition, there is a brief set of questions that caregivers can answer to assess their own level of stress.
 
Step two: The interventionists will next illustrate how caregivers can use the RESCUE website and problem-solving approach to handle stress and depression. For example, the interventionists will use the module and discuss the following: 1) potential causes of stress (e.g., no time for self, disruptive behavior of survivor), 2) setting realistic goals (e.g., allowing one hour each day to do something fun), 3) where to find information on all possible solutions to reach the goal (e.g., RESCUE factsheets "Getting Help" "Taking a Break from Caregiving," and "Additional Resources"), 4) choosing the best solution, 5) evaluating the plan
 
Step three: Throughout the instruction, the interventionists will emphasize the importance of having a positive attitude, state that most caregivers experience depression/stress and that there are effective strategies or treatments available. At designated intervals, the interventionists will ask scripted questions to assess the caregivers' understanding and allow time for questions and explanations.
   |
| 
Topic 3: Individualized Practice Exercise Session
 
Developing a Personalized Problem-Solving Plan
   | 
The interventionists will assist the caregivers in developing their own personalized plans.
 
Step one: The interventionists and the caregivers together will identify all potential problems. To accomplish this step, the interventionists will use motivational interviewing[56] and encourage the caregivers to talk about their uncertainties and what problems they expect to face when their survivors go home. The interventionists will use information learned from the Veterans' health record to help caregivers identify problems. As needed, the interventionists will review the list of 45 topics/factsheets that are on the RESCUE website to trigger identification of problems.
 
Step two: Caregivers will use the "RESCUE workbook" that includes a "problem-solving diary." The caregivers with guidance from the interventionists will use the diary to write down all their problems, prioritize problems, and identify the most troublesome problem. This problem-solving diary can be accessed and printed from the RESCUE website.
   |

|  |   |
|--|---|
| (Sessions 3 - 7)  | Step three: The caregivers will read and discuss the factsheet (s) on the RESCUE caregiver website related to their most troublesome problem. With guidance from the interventionists, the caregiver will use the problem-solving diary to list realistic goal(s), possible solutions, best solution, and evaluation plans.  |
| Topic 4: Summary of the Problem-Solving Method (Session 8) | The interventionists will summarize the content from the previous sessions and answer questions for clarification. The interventionists will encourage the caregivers to use the problem-solving approach and diary to address future problems. The interventionists will review log-on procedures (see details under "workbook" section) and how to navigate and find information and tools on the RESCUE website. |

**RESCUE Problem-Solving Diary Form:** As noted in the table, the interventionists will collaborate with the caregivers in writing their personalized plans on a problem-solving diary. The form provides spaces for the caregivers to list and prioritize their problems and spaces for their goals, solutions, and evaluations. Caregivers will be instructed to go to the RESCUE website and print the blank diary forms as needed. We will mail workbooks to caregivers in the intervention group.

**Standard Care Group:** Will consist of caregivers who receive the care that is normally provided to stroke caregivers of Veterans. No changes will be made in the care that these caregivers normally receive. We will carefully document all follow up care (after Veterans' discharge) by reviewing the Veterans' record and asking caregivers to discuss any care they or their Veteran received. According to clinicians who provide services in the VACHS to Veterans with stroke and their caregivers, once the Veteran is discharged to the home, caregivers do not normally receive any follow-up telephone or transitional care unless they are enrolled in the Telehealth or home-based primary care programs (study exclusionary criteria). Stroke caregivers may only receive contact information for stroke clinicians and some may receive informational brochures or an invitation to participate in an open support group led by the psychologist in the rehabilitation clinic. At the end of the study, we will ask caregivers in the standard care group about resources used throughout the study.

**Fidelity Considerations:** We will make special effort to enhance, maintain and track treatment fidelity. We will use recommendations of Borelli, et al.,[63] and Burgio et al.[64] as our guide. We will adapt the standardized manuals and protocols that were used in our pilot project. This manual will provide step-by-step guidelines on recruiting/enrolling participants, implementing the informed consent process, in conducting the intervention and implementing the data collection procedures. We will provide extensive training to all of our team members. [name] will periodically observe the interventionists conducting the telephone intervention. We will have monthly meetings with the interventionists to discuss implementation of the intervention and discuss protocol issues. To monitor the delivery of the intervention we will audio-tape (digitally record) 10% of the telephone sessions throughout the duration of the project with oral consent from the study participants (Consent will be obtained orally because we are requesting a HIPAA Waiver and Waiver of Documentation for Informed Consent). We will also record the number of minutes spent with each participant and to keep detailed notes of any deviations from our study protocol. The PI and data collector will review these audiotapes and evaluate adherence to study protocols, noting all deviations on a form. Feedback will be provided as needed.

Similar to Bakas, et al.,[23] we will evaluate "enactment" by asking caregivers (in intervention group) after completion of the study (at 12 week post-intervention time-point) to rate the amount of information and contact they received during the 8-session intervention, how much they used the skill-building strategies and the RESCUE website, how helpful the intervention was and whether their problems were resolved.

**Measures:** We carefully chose measures that had been translated into Spanish, used in previous research studies, had good psychometric properties, were easy to administer, and were relatively short in length to reduce participant burden. Most of the measures selected were tools that our team members had used previously in other studies. In the table below, we describe the measures we will use for screening caregivers to determine their study eligibility as well as the measures related to testing hypotheses 1-3. Our other measures are described in later sections. See proposed instruments below.

| Instruments/Measures         |                                   |           |
|------------------------------|-----------------------------------|-----------|
| Concept – Instrument/Measure | Description of Instrument/Measure | Mean Time |
|                              |                                   |           |

| Screening Instruments   |  |             |
|---|--|-------------|
| Veterans' Activity of Daily Living – Stroke Impact Scale   | This tool consists of 16 items that measure patients' abilities to perform self-care tasks (e.g., feeding, bathing, personal toileting, dressing, chair/bed transfers, ambulation). The tool has been used extensively in studies of outcomes of care in rehabilitation settings. We will screen caregivers by asking them if their stroke survivor needs assistance performing the tasks.    | <4 minutes  |
| Perceived Stress Scale – PSS4 (Spanish)   | This is a 4-item 5-point Likert scale ranging from never (0) to very often (5) used to evaluate level of perceived stress. It is ideal to be used as a screening tool for caregiver stress prior to study enrollment and the shortened 4 item version has good psychometric properties.  | <2 minutes  |
| Caregiver Measures  |  |             |
| Demographic and Health Characteristics   | Age, sex, marital status, educational level, race/ethnicity, relationship to stroke survivor will be collected by self-report.   | <5 minutes  |
| Depressive Symptoms - Center for Epidemiologic Studies Depression (CES-D 20, Spanish Version) | CES-D is a 20-item, 4-point Likert scale ranging from never (0) to most of the time (3). It is assesses depressive symptoms and is not a clinical measure of depression.  Scores range from 0-60 with higher scores indicating greater depressive symptoms. It has been used in numerous studies with caregivers and has good reliability and validity.    | <8 minutes  |
| Problem-Solving Abilities - Social Problem-Solving Inventory - Short Form (SPSI-SF)          | The SPSI-SF is a 25-item tool consisting of five subscales (positive problem-solving orientation, rational problem-solving orientation, negative problem-solving orientation, impulsivity or carelessness style problem solving, avoidance style problem solving). A total score or separate scores can be obtained. Scores range from 0-20 for subscales. The internal consistency of the tool is good. We chose this tool because it has been used in previous, stroke caregiver studies, it has good psychometric problems, and it is briefer than the original 52-item tool.   | <12 minutes |
| Self-Efficacy – Caregiver Self-Efficacy(Spanish)  | This is a 15-item measure of caregivers' judgments regarding their ability to perform effectively in specific, caregiving settings. The measure is composed of two sub-scales: Caregiver Self-Care Efficacy and Caregiver Problem-Solving Self Efficacy. Respondents rate their level of confidence for each item on a scale from 0 to 100. The tool has established reliability and validity.  We selected this self-efficacy tool because it was developed specifically for caregivers and has two subscales that are related to our problem-solving framework.   | <5 minutes  |
| Caregiver Burden –Zarit Burden Interview (S-ZBI, Spanish Version)                             | This is 22-item instrument that has been reduced from the original, full 29-item instrument.  The 22-item version was correlated with the full version with correlation coefficients ranging from 0.92 to 0.97. The ZBI measures the degree of burden felt by caregivers. Items fall into five categories (health, well-being, finances, social life, relationship with impaired person). The instrument was originally developed to measure burden of caregivers of patients with dementia. However, the S-ZBI has been used in stroke caregiver studies. We selected this tool above other burden instruments because it is brief, easy-to-answer, measures both subjective and objective burden, and is a widely-used.  | <12 minutes |
| Quality of Life – VR-12 RAND 12-Item Health Survey v2 (Spanish Version)                       | The VR-12 is a multi-use, self-administered health survey comprised of 12 items. The instrument is primarily used to measure health related quality of life, to estimate disease burden and to evaluate disease-specific benchmarks with other populations. It uses of five-point response choices for the questions that comprise two scales: "Physical Health Summary Measure" and "Mental Health Summary" Measure". The VR-12 has good psychometric properties.    | <10 minutes |
| Problem Checklist  | This instrument was created for the study. The instrument asks caregivers to indicate what problems they or their Veterans are dealing with.   | <5 minutes  |
| Veteran Measures  |  |             |
| Demographic and Health-related variables   | Age, gender, race/ethnicity, facility from which Veteran received stroke related services (i.e., hospital, community living center, rehabilitation), length of rehabilitation, date/location/type of the stroke, and number of previous strokes will be obtained from CPRS review.   | N/A         |
| Functional Abilities – Stroke Impact Scale (Translated)                                       | The Stroke Impact Scale is comprised of 16 short questions and is used assess physical function of patients with stroke.   | <2 minutes  |

|  |  |            |
|--|--|------------|
| Healthcare Utilization – Unintended hospital bed days of care, number of emergency room visits, number of unscheduled clinic visits | Data on healthcare utilization will be obtained from the CPRS records. We decided to measure healthcare utilization in CPRS rather than obtaining similar data that could be found in the Patient Treatment File (PTF) after communicating with staff in the VA Office of Quality Improvement (OQI). The data collector will record the number, dates, and the reasons for all healthcare visits (hospitalizations, ER, clinic visits). Drs. [name] and [name] will review the RA's notes and through consensus decide on which visits were unintended and unscheduled. | N/A        |
| Cost Data – See Aim #3  | We will obtain the standard cost data from the VA Managerial Cost Accounting System (MCAS) (formerly DSS) National Data Extracts (NDE) (total, nursing, pharmacy, laboratory, etc.) by fixed and variable categories and the VA-fee basis files.   | N/A        |
| Measures to check fidelity (see section on Fidelity)/internal consistency   |  |            |
| Enactment (Translated)  | We will use Bakas, et al.,  survey and ask caregivers in the intervention to rate the amount and value of the information they received (see section on fidelity).  | <5 minutes |
| Used Resources Survey   | We will ask caregivers to disclose any resources they used to help them during the duration of the study.   | <3 minutes |

**Data Analysis:** Sample Size and Power Analysis: The sample will consist of 227 caregivers. Our pilot data showed 3.1 points reduction in CESD with a within group standard deviation of 8.9. Assuming such an intervention effect size on depression, 145 subjects per group would achieve 80% power to detect the difference at a 5% significance level. The sample size of 145 per group (intervention vs. standard care) was selected to account for the occurrence of a (10%) dropout rate. The 10% drop-out rate is a conservative estimate of attrition and is based on our pilot study led by our Collaborator [name]. The assumed effect size and variability were deemed reasonable based on a number of other sources. Radloff [66] described large changes pre and post treatment in a clinical setting, with depression from time of admission to 4 weeks post decreasing 20 points for “recovered” patients and 12 points for “still ill” patients. Grant et al.,[24] in a study of a telephone intervention to family caregivers of stroke caregivers, found an estimated 1 month treatment effect of 3.1.

**Aim #1 - Hypothesis #1 (primary):** Stroke caregivers who receive the intervention will have less depressive symptoms at 1 and 12 weeks post-intervention compared to stroke caregivers in the standard care group. Our primary endpoint is the caregiver depressive score. The focus of the primary analysis will be to examine the effect of the intervention based on “intention to treat.” Data from all the participants will be part of the primary analyses regardless of actual number of completed sessions. As an exploratory study element, we will assess compliance and attempt to determine its effect on study results. For the primary analysis, the general linear mixed model for repeated measures will be used to model the follow-up depression times (1 and 12 weeks post-intervention), adjusted for baseline scores as fixed effects. Let  $y_{ij}$  be the depression score for person  $i$  at time  $j$ , then basic fixed effects model will be:

$$E(y_{ij}) = \beta_0 + \beta_1 \text{Baseline}_i + \beta_2 \text{Time}_{ij} + \beta_3 \text{Group}_i + \beta_4 \text{Group}_i * \text{Time}_{ij}$$

with covariates for baseline depression (Baseline), time (Time=0 for 1 week, 1 for 12 weeks post-intervention), and group (0 if active control, 1 if intervention). In order to control for possible chance sample imbalances resulting from randomization, the model will include covariates for baseline prognostic factors (e.g., discharge from hospital, community living center, or rehabilitation facility; caregivers’ relationship to Veteran; number of previous strokes among Veterans, etc.), deemed to have significant relationships with response and groupwise imbalances. Thus, analyses will be able to compare the groups on the measure of interest while controlling for these factors. The primary outcome of interest will be the immediate post-intervention effect at 1-week post-intervention with the 12-week post-intervention as a secondary outcome. This will be tested based on linear contrast  $\beta_3 + \beta_4$  at two-sided 0.05 level. All tests will be performed at the  $\alpha=0.05$  significance level. The correlation among observations from the same person will be accounted for through the inclusion of a random person effect into the mixed model analysis.

**Aim #2 - Hypotheses #2 (secondary):** Stroke caregivers who receive the intervention will have superior outcomes (i.e., less burden, better problem solving skills, greater self-efficacy, and better HRQOL,) at 1 and 12 weeks post-intervention than caregivers in the standard care group. The analysis plan for Hypothesis 2 will closely follow the plan outlined above for Hypothesis 1 for each secondary outcome of interest.

**Aim #3 - Hypotheses #3 (secondary):** Veterans whose caregivers receive the intervention will have better functional abilities at 1 and 12 weeks post-intervention and less healthcare utilization at 12 weeks post-intervention measures compared to Veterans whose caregivers are in the standard care group. Since the score for the Stroke Impact Scale can be treated as a continuous, the analysis plan follows exactly as above in Hypothesis 1. Since the Veteran healthcare utilization measures are count data, the models will be a somewhat different. There will be no baseline covariates added to the model, as they are not applicable to the count measures. Analyses will be conducted for the period following baseline to 12 weeks post-intervention assessments. Generalized linear models for count data (such as Poisson or negative binomial regression models, depending on the presence or absence of over-dispersion) will be employed to determine the group effects on healthcare utilization. Log link functions will be employed on the count data to create the correct distributional data forms. As before, in order to control for possible sample imbalances resulting from randomization, all models will include covariates for prognostic factors deemed to have significant relationships with response and significant groupwise imbalances. Thus, analyses will be able to compare the groups on the measures of interest while controlling for these factors.

**Handling of Missing Data:** In our pilot study we had little missing data with a missigness rate between 0 and 10% depending on measure. Our data collectors will receive extensive training on interviewing and how to politely encourage participants to answer all questions on research instruments. Moreover, the measures quality of life have methods for imputing missing scores on individual items. In the event of drop-outs, the missingness mechanism will be explored. If the assumption of Missing Completely at Random (MCAR) or the common assumption of Missing at Random (MAR) are plausible, then little change to the analysis plan is necessary. The mixed models analysis using direct-likelihood approaches will be unbiased and appropriate. Mixed effects modeling requires large samples, but does not require full data on each subject.[78,79] Study efficiency (power) will of course be affected by the smaller amount of available information, thus we have inflated the planned recruitment sample size. If the missingness assumptions are not plausible, then Missing Not at Random (MNAR) techniques will be employed [80,81] and analysis results will be interpreted with caution.

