## 5. Specific Aims:

**Aim #1:** to test the effect of an 8-session telephone and online problem-solving intervention on stroke caregiver's depressive symptoms at 1 and 12 weeks post-intervention.

**Aim #2:** to test the effect of the intervention on stroke caregivers' burden, self-efficacy, and health-related quality of life (HRQOL) at 1 and 12 weeks post-intervention.

**Aim #3:** to test the effect of the intervention on Veterans' outcomes: Functional abilities and healthcare utilization (i.e., unintended hospital bed days of care, number of emergency room visits, number of unscheduled clinic visits) at 1 and 12 weeks post-intervention.

**Aim #4:** to determine the intervention's budgetary impact.

**Aim #5:** Determine the acceptability of the intervention and the facilitators and barriers that Spanish-speaking stroke caregivers perceive when participating in the study.

We will conduct a two-group randomized controlled trial with repeated measures (baseline, 1 week post-intervention and 12 weeks post-intervention) and use mixed methods to determine caregivers' perceptions of the value, facilitators, and barriers to participating in the intervention. We will enroll 227 caregivers of Veterans with strokes. The caregivers will be recruited from the VACHS in San Juan, Puerto Rico, the James A. Haley Veteran's Hospital in Tampa, FL, and the Orlando VA Medical Center (VAMC) in Orlando, FL. Eligible caregivers

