## 6. Research Plan:

### Research Design and Methods Overview (Aims # 1, 2, 3).

Aim #1: (Primary Aim): to test the effect of an online and telephone support/Internet intervention on Spanish-speaking stroke caregiver's depressive symptoms at 1 and 12 weeks post-intervention.

Aim #2: to test the effect of the intervention on stroke caregivers' burden, self-efficacy, and health-related quality of life (HRQOL) at 1 and 12 weeks post-intervention.

Aim #3: to test the effect of the intervention on Veterans' outcomes: Functional abilities and healthcare utilization (i.e., unintended hospital bed days of care, number of emergency room visits, number of unscheduled clinic visits) at 1 and 12 weeks post-intervention.

Design: We will conduct a two-arm (intervention vs standard care), randomized controlled clinical trial (RCT) with three assessment points (baseline, 1 week post-intervention and 12 weeks post-intervention).

Study Location: Study participants will be recruited from the VA Caribbean Healthcare System (VACHS) in San Juan, Puerto Rico, James A. Haley Veteran's Hospital in Tampa, FL, and the Orlando VA Medical Center (VAMC) in Orlando, FL, but all study procedures will be conducted over the phone from either the North/Florida South Georgia Veterans Healthcare System (NF/SG VHS) in Gainesville, FL or the VACHS in San Juan. The James A. Haley and Orlando VAMC sites serve only as identification and referral sites.

Sample: The sample will consist of 227 Hispanic caregivers of Veterans with strokes, 21 years old or older who will be randomized to one of two study arms. In addition, we will conduct chart reviews on the 227 corresponding Veterans.

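### Enrolment is 227, but the only power statement is for 145 per group (290 in total); no power is given for 227, and the plan's own calculation gives about 70–74% there

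*Combined protocol and SAP*

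**What the plan says.** Three places fix the enrolment:

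- Section 5, Specific Aims: "We will enroll 227 caregivers of Veterans with strokes".
- Section 6, Sample: "The sample will consist of 227 Hispanic caregivers of Veterans with strokes", and for the paired Veterans "we will conduct chart reviews on the 227 corresponding Veterans".
- Section 6, Data Analysis, Sample Size and Power Analysis: "The sample will consist of 227 caregivers".

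That last paragraph then justifies a different size. It gives the inputs, "Our pilot data showed 3.1 points reduction in CESD with a within group standard deviation of 8.9", and states that "145 subjects per group would achieve 80% power to detect the difference at a 5% significance level". It adds that "The sample size of 145 per group (intervention vs. standard care) was selected to account for the occurrence of a (10%) dropout rate", so dropout is already inside the 145.

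Under Aim #1, Hypothesis #1, the primary test is "at two-sided 0.05 level", from a mixed model with baseline depression as a covariate. The primary time point is 1 week post-intervention. Handling of Missing Data says that planned recruitment was increased to allow for lost information. The recruitment text forecasts 8 caregivers a month for 36 months.

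**The concern.** A trial's sample size and its stated power have to describe the same trial. Here the 80% is attached to 290 caregivers and the enrolment is 227. Both numbers stand in one paragraph with no link between them. The 145 cannot be read as a total, because the text says that it is per group.

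This paragraph is the only sample-size justification for the primary endpoint. If the trial finds no effect on depressive symptoms, readers will use the 80% to judge how informative that result is, and the figure does not apply to the trial that was run. If 227 has a sound basis of its own, the protocol does not record it.

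**Working it through.** **Inputs.** From the sample-size paragraph: difference 3.1 CES-D points, SD 8.9, 80% power, 5% level, 10% dropout. From Hypothesis #1: two-sided 0.05. Allocation is taken as 1:1. No ratio is stated, but the blocks are meant to balance the groups and the plan uses 145 in each. Standardised difference: 3.1/8.9 = 0.348.

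**Step 1: reproduce 145.** For a two-sample comparison of means,

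n per arm = 2 × (1.960 + 0.842)² × 8.9² / 3.1² = 129.4, so 130 (130.4 with the t distribution).

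130/0.9 = 144.4, so 145 per arm. The totals are 2 × 130 = 260 evaluable and 2 × 145 = 290 enrolled. The stated figure is matched.

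**Step 2: compare with 227.**

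- Enrolled: 290 − 227 = 63 fewer.
- Evaluable after 10% dropout: 227 × 0.9 = 204.3, so about 204 (102 per arm), against 260 needed; 56 fewer.
- Even with no dropout, 227 is 260 − 227 = 33 below the evaluable number. On this calculation, 227 therefore contains no allowance for dropout, contrary to Handling of Missing Data.

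**Step 3: the same calculation at 227** (two-sided t-test; normal approximation in brackets).

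| Evaluable per arm | Power for 3.1 points | Difference detectable at 80% | SD giving 80% for 3.1 points |
|---|---|---|---|
| 130 (the plan's basis) | 79.9% (80.2%) | 3.1 | 8.9 |
| 113.5 (227, no dropout) | 74.3% (74.7%) | 3.32 | 8.30 |
| 102 (227, 10% dropout) | 69.7% (70.1%) | 3.51 | 7.86 |

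**Step 4: the planned baseline-adjusted analysis.** Treat it as an analysis of covariance at one follow-up, with equal variances over time and correlation r between baseline and follow-up. The residual SD depends on what 8.9 is:

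- raw-score SD: 8.9 × √(1 − r²)
- change-score SD: 8.9 × √((1 + r)/2)
- already baseline-adjusted: 8.9

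The plan gives no r, so the values below are assumed.

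| Meaning of 8.9 | 102 per arm, r = 0.4 / 0.5 / 0.6 | 113.5 per arm, r = 0.4 / 0.5 / 0.6 |
|---|---|---|
| Raw score | 77.1 / 81.6 / 87.2% | 81.4 / 85.5 / 90.4% |
| Change score | 84.1 / 81.6 / 79.0% | 87.8 / 85.5 / 83.2% |
| Already adjusted | 69.7% at any r | 74.3% at any r |

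**Step 5: can 227 be derived another way?** With a one-sided 0.05 test and otherwise the same inputs, n = 2 × (1.645 + 0.842)² × 8.9² / 3.1² = 101.9, so 102 per arm, and 204/0.9 = 226.7, which rounds to 227. No section states this, and it conflicts with the two-sided primary test.

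**The case against.** The strongest reply is that 70–74% belongs to an unadjusted two-sample test, which is not the planned analysis. With baseline adjustment, power at 227 could well reach 80%: at 102 per arm it is 77–87% if 8.9 is a raw-score SD and 79–84% if it is a change-score SD, over the assumed correlations. This stands, and it is why no shortfall is claimed for the planned model. It does not rescue the 80% statement, because the plan documents neither the SD type nor a correlation.

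Second, 102 per arm may be pessimistic for the primary time point. The 10% dropout is not tied to a visit, and a caregiver lost after the 1-week assessment still contributes primary data. That is fair; the no-dropout column is the upper bound, and on the plan's own calculation it still reaches only 74.3%.

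Third, the one-sided match would make 227 a figure properly inflated for dropout. It may be the origin of 227 or a coincidence. If it is the origin, the sample size and the primary test use different error rates, and that too needs correcting.

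Fourth, 227 is used consistently as the enrolment figure, so what will be enrolled is clear and only documentation is at fault. That is true of enrolment. The power claim is still wrong for that enrolment.

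**Conclusion.** The concern holds. The plan gives two incompatible sizes for one trial, 227 and 290, and its only stated power belongs to the larger. On the plan's own two-sample calculation, 227 gives about 70% power with the planned 10% dropout and 74% with none, or 80% power for about 3.5 or 3.3 points instead of 3.1. These figures rest on 1:1 allocation, the two-sided 0.05 level and SD 8.9 used as the plan used it. Power of the baseline-adjusted model at 227 cannot be worked out from the documents: it could be about 70% or above 80%. A shortfall in that analysis is therefore not shown; what is shown is that the stated 80% is unsupported for 227.

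**What to change.** Reconcile 227 with 145 per group in the sample-size paragraph, state the basis for the number kept (including whether 227 came from a one-sided calculation), and make the power statement match it. If 227 stands, replace the sentences on 145 per group with text such as:

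> 227 caregivers will be enrolled; about 204 (102 per arm) are expected to be evaluable after 10% dropout. In a two-sample comparison at two-sided 0.05 with SD 8.9, this gives about 70% power for 3.1 points and 80% power for about 3.5 points.

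Then:

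- State whether 8.9 is a raw-score, change-score or baseline-adjusted SD. If baseline adjustment is relied on for more power, give the assumed correlation and the resulting power beside the two-sample figure.
- Bring the inflation statement in Handling of Missing Data into line with the number kept.
- As side points on which the conclusion does not rest, align the accrual forecast (36 × 8 = 288, close to 290; 227 would take 227/8 = 28.4 months), and reconcile its 36 months with the statement earlier in the recruitment text that recruitment runs to the end of year 05.

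If 227 is kept, the cost is wording only: enrolment, test and model do not change. The stated power becomes less favourable unless the sponsor can document the SD type and correlation.
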